Potential benefits of intermediate-dose vs. prophylactic dose anticoagulation	
 • Potential for reduced risk of thrombotic complications (including VTE, MI, stroke, and line thrombosis) • Potential for improving the recovery from need from mechanical ventilation. • Potential for reducing the risk of DIC. • Potential for reducing the risk of renal failure. • Potential for reducing mortality as a result of reducing the above components.
Potential risks of intermediate-dose vs. prophylactic dose anticoagulation	
 • Increased risk of bleeding, including major bleeding • Heparin induced thrombocytopenia

VIII. Study Design and Analysis Plan (include timing and primary and secondary endpoint analysis)

In order to assess event rates and appropriately adjust study measures as part of adaptive trial design, a blinded interim analysis at the combined event rate of both study arms will be performed. Once the trial is completed, analysis will be performed by intention to treat.

General Design

This is a cluster randomized-controlled clinical selection trial of interventions for anticoagulation for COVID-19 patients in the ICU. ICU subunits will be randomly assigned to give patients intermediate (higher) dose or prophylactic (lower) dose of anticoagulation. The primary goal of the trial is to select the best intervention with a high probability of *correct* selection if one intervention is truly superior by a pre-specified effect size. Up to 100 patients (with expected sample sizes between 69-75 patients for the most likely scenarios) will be enrolled in the study, using a novel sequential design. Each time an outcome is observed for a patient, those outcomes are added to a running tally of successes for each intervention. There is a pre-specified criterion in terms of the success tallies for selecting arm as evidence of apparent superiority accumulates. With this sequential procedure, the preferred intervention can be selected during the ongoing enrollment as soon as the pre-specified selection criteria are met, and further enrollment will cease. To ensure that there will be some unbiased estimates of the proportion of patients with a good outcome available for each intervention arm, the selection criteria will not be applied until 60 patients have been observed. This novel approach based on the Levin-Robbins-Leu family of sequential selection procedures [18-23].

Study Implementation

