The identification of a preferred treatment will be done using an innovative sequential selection procedure, which will substantially reduce the number of patients in comparison to a hypothesis test procedure. The data will be examined each time a pair of patients completes follow-up after 60 patients have been observed.

The goal of the procedure is to make a correct selection with high probability. The procedure follows the preference zone / indifference zone approach, wherein we require the selection procedure to guarantee a probability of at least 90% *correct* selection (of the truly best intervention), assuming that one is truly superior to the other by a pre-specified amount. This pre-specification defines a region in the parameter space called the *preference zone*. If the best intervention does not exceed the next best by the pre-specified amount, the success probabilities are said to lie in the *indifference zone*, where we shall be indifferent to the fact that the probability of correct selection may be less than 90%. For this trial, the preference zone consists of all parameter vectors (p_1, p_2) of success probabilities where the odds ratio comparing the largest to the next largest is greater than or equal to 2.15 ($p_1=0.35, p_2=0.20$).

The selection procedure is specified by the sampling rule, the stopping rule, and the terminal decision rule, as follows.

Sampling rule: Patients, when eligible, will be enrolled to the study at the “first-come-first-serve” basis. All the participating ICUs can have 2 possible “room type”: negative pressure rooms and non-negative pressure rooms. Each of the participating ICUs will be divided into either two or four clusters as follows. Any ICU with only one room type (i.e., it only has negative pressure rooms or only has non-negative pressure rooms) will be divided into 2 clusters. For ICUs that contain both room types (i.e., it has negative pressure rooms and non-negative pressure rooms), we will divide that ICU into 4 clusters with two clusters for each room type. Two clusters within each ICU and each room type will then be randomized to either of the study arms. Enrolled patients will receive

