If at the time of stopping there are partially filled or partially observed pairs of patients that have been randomized and have started their intervention, we will allow each patient in each such pair to complete their follow-up even if the arm to which they were randomized is eliminated.

Operating characteristics: In Appendix, we calculate the operating characteristics for various scenarios via simulation study with 100,000 replications. Operating characteristics include the probability of correction, the expected total number of patients, the expected total number of patients with bad outcome, the probability that the trial will be truncated before reaching the criterion for stopping, the probability of reaching a decision after exactly 60 patients (30 in each arm), the probability of correct selection after exactly 60 patients (30 in each arm), and the conditional probability that correct selection is made given that exactly 60 patients (30 in each arm). Scenarios discussed cover the parameters in the preference zone, in the indifference zone, and the null case (i.e., $p_1=p_2$).

Analysis of the Primary Endpoint with the Full Sample

In general, a selection procedure, unlike a hypothesis test procedure, is not specifically designed to provide a *p*-value below a conventional level of significance. Indeed, we will *not* be declaring any differences statistically significant, as that is explicitly *not* the goal of the present selection trial, i.e., we are explicitly *not interested* in testing the null hypothesis of no differences between the interventions. Instead, because the adaptive sequential selection procedure can be described as a procedure that samples until there is a pre-specified *weight of evidence* for making correct selections, assuming there is a minimum true degree of superiority as measured by the design odds

ratio, we will quote the *likelihood ratio (LR) measure of weight of evidence* in various ways. Details regarding how the LR was calculated and examples to illustrate their interpretations can be found in the supplemental appendix.

Endpoint Evaluation

All patients will be evaluable for ischemic outcomes and bleeding from the time of their first treatment with the anticoagulant.

Analysis of Primary Endpoint and Secondary Endpoints for the first 60 patients

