To avoid bias in statistical inference due to bias in sampling, *only* the first 60 patients will be included in this set of analysis. Details explain why bias occurs and how it will affect the statistical inference can also be found in the supplemental appendix. We will use the data from these 60 patients to generate the proportions of patients with the events specified as primary and secondary outcomes. We will also report the descriptive statistics (mean, median, interquartile range) for the time to ICU discharge. Graphical display of the data will be done as well. To compare the intervention effect between the two study groups on the primary and secondary outcomes, we will use generalized linear model with identity link function for continuous variables and logit link function for dichotomous variables following the intent-to-treat principle. Covariates in these models include intervention group indicator, ICU indicators, and the potential confounding factors. The pre-specified potential confounders are age, sex, weight, estimated glomerular filtration rate (eGFR), concomitant treatment with an IL-6 inhibitor, and concomitant treatment with corticosteroids. Generalized estimating equations methodology will be employed to account for the within-ICU correlation for subject assignment to the same ICU area. The key parameter of interest is the regression coefficient corresponding to the intervention group indicator which is the mean difference for continuous outcomes and log-odds ratio for dichotomous outcomes and it represents intervention effect of intermediate-dose anticoagulation compared with that of prophylactic anticoagulation. To report the trial findings, we will present the mean difference and odds ratio when appropriate and their corresponding p-values and 95% confidence intervals. Several pre-specified sensitivity analyses will be conducted: (1) excluding the patients who undergo CRRT during the study period; (2) excluding patients who experienced deviation in anticoagulation from randomized treatment arm; (3) analyzing the patients as the treatment they actually received. Additional sensitivity analysis will also be conducted to include covariates found imbalanced between the two intervention groups.

Operating characteristics of the Study Design

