The stopping criterion of a lead of at least 4 between largest and smallest success tallies was chosen to achieve a probability of correct selection of at least 90% for any true success probabilities lying in the preference zone characterized by an odds ratio of 2.15 or greater between the true success probabilities of the two interventions. For example, true success probabilities of 0.35 and 0.20 with an odds ratio of 2.15 is lying on the boundary between the preference and indifference zones. For any such configuration with $\{p_1/(1-p_1)\}/\{p_2/(1-p_2)\} = 2.15$, the selection procedure will result in a correct selection with at least 90% probability. Table 1 shows the operating characteristics of the selection procedure under various scenarios of true success probability configurations for the two arms.

TABLE 1
Operating characteristics of the selection procedure

Scenario 1. $p_1=0.35$, $p_2=0.20$, criterion for stopping is a difference of 4 between the tallies, truncation at 100 patients, minimum # of patients before possible selection=60						
ET	EF	PCS	P[truncation]	P[T=T ₀]	P[T=T ₀ ,CS]	P[CS T=T ₀]
68.4	49.6	95.1%	10.2%	62.6%	61.6%	98.4%
Scenario 2. $p_1=0.30$, $p_2=0.20$, criterion for stopping is a difference of 4 between the tallies, truncation at 100 patients, minimum # of patients before possible selection=60						
ET	EF	PCS	P[truncation]	P[T=T ₀]	P[T=T ₀ ,CS]	P[CS T=T ₀]
74.0	55.5.4	87.1%	21.5%	46.6%	44.0%	94.5%
Scenario 3. $p_1=0.20$, $p_2=0.20$, criterion for stopping is a difference of 4 between the tallies, truncation at 100 patients, minimum # of patients before possible selection=60						
ET	EF	PCS	P[truncation]	P[T=T ₀]	P[T=T ₀ ,CS]	P[CS T=T ₀]
83.0	66.4	50.2%	43.5%	25.7%	12.9%	50.2%

ET is the expected total number of patients

EF is the expected total number of patients with bad outcome

PCS is the probability of correct selection

P[truncation] is the probability that the trial will be truncated before reaching the criterion for stopping

P[T=T₀] is the probability of reaching a decision after exactly 60 patients (30 in each arm)

P[T=T₀, CS] is the probability of correct selection after exactly 60 patients (30 in each arm)

P[CS|T=T₀] is the conditional probability that correct selection is made given that exactly 60 patients (30 in each arm)

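### Table 1 and the 90% correct-selection statement assume independent patients although room clusters are randomised, and truncation makes the 90% untrue at extreme success rates

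*Combined protocol and SAP*

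**What the plan says.** The General Design section sets the unit of randomisation: "ICU subunits will be randomly assigned to give patients intermediate (higher) dose or prophylactic (lower) dose of anticoagulation". The sampling rule adds that each ICU and room type holds two clusters, which are randomised to the arms.

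The Study Implementation section requires at least 90% probability of correct selection throughout the preference zone. The section on operating characteristics of the study design names the boundary: "true success probabilities of 0.35 and 0.20 with an odds ratio of 2.15 is lying on the boundary between the preference and indifference zones". For every pair at that odds ratio it then states that "the selection procedure will result in a correct selection with at least 90% probability".

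The support for this is Table 1. The plan says of it: "we calculate the operating characteristics for various scenarios via simulation study with 100,000 replications". Each scenario lists the two success probabilities and the rule: "criterion for stopping is a difference of 4 between the tallies, truncation at 100 patients, minimum # of patients before possible selection=60". No ICC, cluster count or design effect appears. The likelihood used for the weight of evidence is likewise a plain product of Bernoulli terms.

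The regression models for the first 60 patients are treated differently: "Generalized estimating equations methodology will be employed to account for the within-ICU correlation for subject assignment to the same ICU area".

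**The concern.** The plan allows for correlation in one analysis and is silent about it in the calculation that justifies the design. In a selection trial, PCS takes the place of power. If patients in the same room cluster have similar outcomes for reasons other than treatment, the success tallies vary more than independent sampling implies, and the wrong arm is selected more often than Table 1 shows. A reader of Table 1 cannot tell that its figures depend on independence.

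The 90% statement is also worded for all success probabilities at the design odds ratio, whereas Table 1 examines only one pair on that boundary. Whether 90% holds elsewhere has to be checked with the truncation at 100 in place.

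**Working it through.** **Inputs from the plan.** Success probabilities 0.35 v 0.20; stop at a lead of 4; first look at 60 patients (30 pairs); truncation at 100 (50 pairs). On monitoring: "The data will be examined each time a pair of patients completes follow-up after 60 patients have been observed".

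**Step 1: reproduce Table 1 under independence.** For one pair, the tally difference D moves up with probability p1(1−p2), moves down with probability p2(1−p1), and otherwise stays. At 0.35 v 0.20 these are 0.35 × 0.80 = 0.28 and 0.20 × 0.65 = 0.13. I ran the exact distribution of D for 30 pairs, then pair by pair to 50. It stops when |D| ≥ 4; the larger tally wins at truncation, and a tie counts one half.

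| Scenario | Quantity | Table 1 | Recursion |
|---|---|---|---|
| 0.35 v 0.20 | PCS | 95.1% | 95.2% |
| | Expected patients | 68.4 | 68.41 |
| | Truncation | 10.2% | 10.4% |
| | Decision at 60 | 62.6% | 62.6% |
| 0.30 v 0.20 | PCS | 87.1% | 87.3% |
| | Expected patients | 74.0 | 73.9 |
| 0.20 v 0.20 | PCS | 50.2% | 50.0% |
| | Expected patients | 83.0 | 83.0 |

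Table 1 is correct for independent patients and contains no clustering. (The paragraph after Table 1 quotes other percentages. That is a separate matter and is not used here.)

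**Step 2: add correlation within room clusters.** Assumptions: K clusters per arm, patients falling into them at random, and beta-binomial outcomes with a given ICC. K and ICC are mine. As a hand check, with 30 patients per arm in 3 equal clusters the design effect at ICC 0.05 is 1 + (10 − 1) × 0.05 = 1.45. At the first look D has mean 30 × 0.15 = 4.5 and independent variance 30 × (0.35 × 0.65 + 0.20 × 0.80) = 11.6. The SD rises from 3.4 to about √(11.6 × 1.45) = 4.1, while the mean is unchanged.

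Simulated PCS at 0.35 v 0.20 (60,000 to 150,000 replicates; repeat runs differ by up to about half a point):

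| Clusters per arm | ICC 0.01 | ICC 0.02 | ICC 0.05 | ICC 0.10 |
|---|---|---|---|---|
| 3 | 93.8% | 92.7% | 89.4% | 85.2% |
| 6 | 94.6% | 94.0% | 92.3% | 89.4% |
| 10 | 94.8% | 94.5% | 93.3% | 91.5% |

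PCS crosses 90% at an ICC of about 0.05 (K = 3), 0.06 (K = 4), 0.09-0.10 (K = 6) and 0.15 (K = 10).

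Other entries:
- Scenario 1 expected sample size stays between 68.4 and 69.3.
- Scenario 2 PCS at ICC 0.05 is 80.1% (K = 3), 83.4% (K = 6) and 84.6% (K = 10), against 87.1% stated.
- Scenario 3 PCS stays at 50%. With K = 3 and ICC 0.05, the probability of a decision at 60 patients rises from 25.7% to 35.4%, and expected patients fall from 83.0 to 79.0.
- In a separate latent-normal simulation, correlation shared by both arms of an ICU left scenario 1 PCS at 95-96%.

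**Step 3: the 90% statement under independence.** Without truncation, PCS would be at least OR⁴/(1 + OR⁴) = 21.5/22.5 = 95.6% for every pair at this odds ratio, because each decision is then made at a lead of 4 or more. Truncation removes that floor when few pairs are discordant:

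| Pair (OR 2.15) | Discordance probability | Expected discordant pairs in 50 | PCS |
|---|---|---|---|
| 0.35 v 0.20 | 0.28 + 0.13 = 0.41 | 20.5 | 95.2% |
| 0.15 v 0.076 | 0.139 + 0.065 = 0.203 | 10.2 | 88.0% |
| 0.951 v 0.90 | 0.095 + 0.044 = 0.139 | 7.0 | 83.3% |

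PCS is 88.5% at p2 = 0.08 and 90.6% at p2 = 0.10. At the upper end it is 90.9% at p2 = 0.80 and 88.0% at p2 = 0.85. The 90% therefore holds for p2 from roughly 0.10 to 0.80. Near those limits there is no slack: at p2 = 0.10, an ICC of 0.01 gives 89.1% (K = 3), 89.7% (K = 6) and 90.1% (K = 10).

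**The case against.** A reader might infer that Table 1 and the 90% figure are simply overstated because clusters are randomised. The documents do not support that, for four reasons.

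- Overstatement requires a positive ICC specific to room clusters, and none is given. The correlation the plan names is within ICU, and each ICU and room type contains both arms, so effects common to an ICU largely cancel. Using generalized estimating equations allows for correlation; it does not assert that correlation exists.
- At 0.35 v 0.20 there are about five points of slack above 90%. At ICC 0.01-0.02 every case tried stays at 92.7% or more.
- Fixed clusters with a lasting effect are a modelling choice. The 3:1 phase is described in terms of rooms, and the ratio later returns to 1:1. If rooms act as many small units, the effect shrinks: at ICC 0.05, PCS is 93.9% with 15 units per arm and 94.6% with 30; at ICC 0.10 it is 92.6-93.8% with 15 to 30.
- Much of Table 1 is not optimistic. Scenario 1 sample size barely moves, null PCS stays at 50%, and null sample size falls.

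All four stand, and they make the clustering point conditional. They do not remove it, because the documents give nothing from which a reader could judge which case applies. The failures in step 3 come from truncation and are no evidence about clustering. The success rates where they occur lie outside those in Table 1, but they lie inside the statement as it is worded.

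**Conclusion.** Table 1 and the 90% statement are calculated for independent patients in a trial that randomises room clusters. PCS in scenarios 1 and 2 is optimistic if outcomes are positively correlated within those clusters. How optimistic is unknown: over the assumed 3 to 10 clusters per arm and ICC 0.01 to 0.10, the loss at 0.35 v 0.20 runs from about 0.3 points (95.1 − 94.8) to about 10 points (95.1 − 85.2). For the design alternative, 90% is unverified under clustering; it has not been shown to be wrong.

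As a statement about every pair at odds ratio 2.15, the 90% is wrong even under independence, because of the truncation. That result needs no assumption beyond the plan's own rule, with ties at truncation counted one half.

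Nothing here shows that the trial needs more patients or a different lead.

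**What to change.** Rerun the Table 1 simulation with outcomes correlated within the actual room clusters, over a stated range of ICCs (for example 0, 0.01, 0.05 and 0.10), and report the number of clusters or rooms per arm that was used. In the Study Implementation section and in the section on operating characteristics of the study design, replace the unconditional 90% with the PCS range and the success probabilities and ICCs for which 90% holds. Sample size and stopping rule do not change. The cost is a rerun of an existing simulation and a slightly less favourable stated PCS.

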Secondary Endpoints	
 Composite of being alive and without clinically-relevant venous or arterial thrombotic events at discharge from the hospital (without transfer to a palliative care unit/hospice) or at 30 days (if hospital stay lasted 30 days or longer) Individual components of the primary outcome in the ICU ICU length of stay Need for renal replacement therapy Major bleeding (assessed by BARC criteria, also explored by ISTH and TIMI criteria) Individual components of the primary outcome during entire hospitalization. Hospital length of stay
Estimated Sample Size	Up to 150 subjects (to be determined by sequential randomized selection design)

[figure not shown]
¹This dose generally does not require routine monitoring of anti-Xa activity, but may be monitored by the primary team outside this study to assess for effectiveness and dose adjusted in consultation with pharmacist

²To be monitored at least 8 hours after the initiation of the infusion or any dose change.

Patients with improving kidney function or new AKI can be switched from one agent to the other within the same intervention group

Acute kidney injury defined as:

- Increase in SCr by ≥ 0.4 mg/dL within 48 hours; or
- Increase in SCr to ≥ 1.5 times baseline, which is known or presumed to have occurred within the prior 7 days; or
- Urine volume <40 mL/h for 6 hours

I. Study Population

Patient Inclusion Criteria	
 • Age >18 years of age • Confirmed diagnosis of COVID-19 by RT-PCR • New admission to eligible CUIMC ICUs within 5 days 
 ○ Transfer from nonparticipating to participating ICU is eligible if otherwise meets eligibility criteria. ○ Patients not on therapeutic anticoagulation and who were already admitted to participating ICU within 5 days of trial initiation are additionally eligible.

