The first scenario corresponds to the abovementioned design alternative which we believe is minimal clinically meaningful and worthwhile. The second scenario describe the operating characteristics of the selection procedure inside the indifference zone, assuming smaller differences in the success rates for the two interventions. The third scenario illustrates a case where there is no true difference in the rates for the two arms.

In scenarios 1 and 2 where there is a superior arm, the design chooses the superior arm over 87% of the time across these scenarios with average sample sizes between 68.4 and 74.0. Under the design alternative, there is 82.5% probability that we will stop the trial with 30 patients per arm. The probability of having to truncate the study ranges from 3.5% to 10.6%, with the lowest probability for our design alternative. The probability of selecting the superior arm at exactly 100 patients are enrolled is between 63.7% and 81.9% in these scenarios, which explains the need to continue enrollment to ensure that the correct dose is selected with high probability. Nevertheless, the conditional probability that correct selection is made given that exactly 100 patients have been randomized is very high (between 96.4% and 99.2%).

In scenario 3, there is no difference between the two arms. Thus, the design randomly selects one of them with a probability of 0.50. However, given that they are all the same, it is acceptable to select any of them and thus the probability of selecting an acceptable intervention is 100%. Because there is no superior intervention in this scenario, evidence of an apparent advantage accumulates more slowly than under other scenarios and thus the procedure incurs a larger average sample size and probability of truncation.

Formula to Calculate the Likelihood Ratio and its Interpretations

At the end of the trial, we will calculate the likelihood of the success tallies. This likelihood is given by

$$L(p_i, p_j | X_i^{(n)}, X_j^{(n)}) = p_i^{X_i^{(n)}} (1-p_i)^{n-X_i^{(n)}} p_j^{X_j^{(n)}} (1-p_j)^{n-X_j^{(n)}},$$

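### Four operating-characteristic figures in the text contradict Table 1 (82.5% against 62.6% for stopping at 60 patients), and the outline gives a maximum of 150 where the design section gives 100

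*Combined protocol and SAP*

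**What the plan says.** Section VIII, Operating characteristics of the Study Design, presents Table 1 for three scenarios, each headed "truncation at 100 patients, minimum # of patients before possible selection=60" and a lead of 4. The Operating characteristics paragraph earlier in that section says of their source: "we calculate the operating characteristics for various scenarios via simulation study with 100,000 replications".

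The paragraph interpreting scenarios 1 (0.35 vs 0.20, the design alternative) and 2 (0.30 vs 0.20) then makes five statements:

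- On overall performance and average size, it says "the design chooses the superior arm over 87% of the time across these scenarios with average sample sizes between 68.4 and 74.0".
- On a decision at the first look, it says "Under the design alternative, there is 82.5% probability that we will stop the trial with 30 patients per arm".
- On running to the cap, it gives a range for both scenarios: "The probability of having to truncate the study ranges from 3.5% to 10.6%, with the lowest probability for our design alternative".
- On a correct choice at the first look, it names a different patient number: "The probability of selecting the superior arm at exactly 100 patients are enrolled is between 63.7% and 81.9% in these scenarios".
- On the conditional value, where both endpoints are percentages, it again names that number: "the conditional probability that correct selection is made given that exactly 100 patients have been randomized is very high (between 96.4% and 99.2".

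For the maximum, the Protocol Outline (Estimated Sample Size) reads "Up to 150 subjects (to be determined by sequential randomized selection design". General Design, the Stopping and Decision rule, and Table 1 all give 100.

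**The concern.** The first bullet agrees with Table 1; the other four do not. Two of those four also refer to 100 patients, where Table 1 defines the same quantities at 60.

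The plan declines to test for significance, so its operating characteristics are what justify the design. The lead criterion among them, the overall probability of correct selection, is stated correctly. The wrong figures concern how soon the trial is likely to stop, how often it runs to the cap, and how far a first-look decision can be trusted. All four errors flatter the design. A monitoring board or ethics reviewer who relied on the paragraph would expect a shorter trial with fewer truncations than the table supports, and one who read only the outline would take the ceiling to be 50 patients higher.

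**Working it through.** **Inputs** (section VIII): p1 = 0.35 or 0.30, p2 = 0.20; lead of 4; first decision at 60 outcomes (30 per arm); then a look at each completed pair; cap of 100 (50 pairs).

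**Method.** Let D be the difference in success tallies. Each pair moves D by +1 with probability p1(1 − p2), by −1 with probability p2(1 − p1), and otherwise not at all.

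- Scenario 1: +1 with 0.35 × 0.80 = 0.28; −1 with 0.20 × 0.65 = 0.13; no change 0.59.
- Scenario 2: +1 with 0.30 × 0.80 = 0.24; −1 with 0.20 × 0.70 = 0.14; no change 0.62.

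The distribution of D is computed exactly after 30 pairs. The trial stops if |D| ≥ 4 and otherwise continues pair by pair to 50 pairs. Ties at the cap are split evenly.

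**Results** (scenario 1; scenario 2). The endpoints of the text's ranges are matched to scenarios in the only order that makes sense.

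| Quantity | Text | Table 1 | Exact, first look 60, cap 100 | Exact, first look 100, cap 150 |
|---|---|---|---|---|
| Stop at first look | 82.5%; not given | 62.6%; 46.6% | 62.6%; 46.6% | 82.5%; 66.1% |
| Truncation | 3.5%; 10.6% | 10.2%; 21.5% | 10.4%; 21.3% | 3.5%; 10.7% |
| Stop at first look and correct | 81.9%; 63.7% | 61.6%; 44.0% | 61.7%; 44.1% | 81.9%; 63.7% |
| Correct, given stop at first look | 99.2%; 96.4% | 98.4%; 94.5% | 98.5%; 94.6% | 99.2%; 96.4% |
| Average N | 68.4; 74.0 | 68.4; 74.0 | 68.4; 73.9 | 104.3; 109.9 |
| Correct selection overall | over 87% | 95.1%; 87.1% | 95.2%; 87.3% | 97.8%; 91.8% |

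Table 1 reproduces. The text's four figures do not fit the stated design, but they fit a first look at 100 with a cap of 150 to within 0.1 point. The averages in the same paragraph belong to the 60-to-100 design.

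**Could it be simulation error?** With 100,000 replications the standard error at 62.6% is √(0.626 × 0.374 / 100,000) = 0.0015, or 0.15 point. The gap is 82.5 − 62.6 = 19.9 points.

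**Could a cap of 150 explain it?** No. The probability of stopping at 60 does not depend on the cap and stays at 62.6%. Truncation would become 2.4% and 7.4%, which is not what the text says either.

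**Consistency within the paragraph.** If 82.5% of trials stop at 60 and none exceeds 100, the average is at most 60 × 0.825 + 100 × 0.175 = 67.0. The paragraph states 68.4 for the same scenario. And if 82.5% stop at 60, at most 17.5% can reach 100, so correct selection at exactly 100 cannot have probability 63.7% or more under the design alternative.

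**Two related points in section VIII.**

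1. The first sentence of the Stopping and Decision rule applies the lead of 4 only up to the 60th outcome. Study Implementation, Table 1 and Minimizing Selection Bias apply it at 60 and at each later pair.
2. The text above Table 1 promises at least 90% correct selection for every configuration with odds ratio 2.15. With the cap at 100 this fails at extreme rates: 83.6% at 0.05 vs 0.102, and about 83% at 0.90 vs 0.951. The 90% line is crossed at worse-arm rates of about 0.093 and 0.819; the value is 90.6% at 0.10 and 90.5% at 0.81.

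**The case against.** The best case for the plan is that nothing operational depends on this paragraph. The correct table stands directly above it. The criterion the design was built on, overall correct selection, is right in both places, as are the average sample sizes. That is true, and it limits the weight of the point: neither the intended rule nor the analysis has to change.

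It can also be said that the exact figures are not the trial's true probabilities. They assume independent outcomes and 30 per arm followed by 1:1 pairs, while patients are clustered in ICUs. This stands as a qualification. The comparison shows that the text misreports Table 1 under Table 1's own model. It does not show that Table 1 allows for clustering.

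On the maximum, 150 might have been meant to cover patients still in follow-up when the trial stops. The outline does not say so, and General Design caps enrolment itself at 100, so the conflict remains.

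The wording about the 60th outcome is largely repaired later in its own paragraph, which truncates only if the criterion has not been met by 100 outcomes. It is a slip to correct, not a second design.

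The failure of the 90% promise lies well outside the planned rates (0.20 for the worse arm), and its exact limits depend on how ties at the cap are broken, which the plan leaves to other considerations. It is a secondary point, but the promise as written covers every configuration.

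**Conclusion.** The concern holds. Four figures are wrong for the stated design, and two of them are attached to the wrong number of patients. Stopping at 60 under the design alternative is overstated by 19.9 points. The implied chance of needing more than 60 patients is 17.5%, where Table 1 gives 100 − 62.6 = 37.4%. Truncation is shown at about a third to a half of Table 1's values (3.5/10.2 = 0.34; 10.6/21.5 = 0.49). The stated maximum differs by 50 patients between the outline and section VIII.

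This should be fixed, but it does not undermine the design: correct selection at the design alternative is 95.2% on exact calculation. The result rests on independent outcomes, 30 per arm and then 1:1 pairs, and an even split of ties at the cap. The figures for stopping at the first look do not depend on the tie rule. That the text's figures were carried over from a 100-to-150 design, and the outline's 150 with them, is an inference from the numerical match; the documents do not say so.

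**What to change.** 1. In the paragraph below Table 1, use the table's figures: 62.6% for stopping with 30 per arm; truncation 10.2% to 21.5%; correct selection at the first look 44.0% to 61.6%; conditional 94.5% to 98.4%. Change 100 patients to 60 in the last two statements.
2. Change the outline's maximum to 100, in line with section VIII, and say whether that figure includes patients in incomplete pairs when the trial stops.
3. Reword the first sentence of the Stopping and Decision rule so that the lead of 4 applies when 60 outcomes have been observed and at each later completed pair up to 100.
4. Limit the 90% promise to worse-arm success rates of about 0.10 to 0.81, or state it for the design alternative only.

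This changes wording and stated figures only. The corrected probabilities are less favourable than those now in the text. No extra patients are needed, and the intended decision rule and analysis stay as they are.
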